6.7 Contraception

Female patients of childbearing potential (defined as < 2 years after last menstruation and not surgically sterile) and their male partners must use a highly effective method of contraception resulting in a low failure rate (i.e. less than 1% per year) during chemotherapy treatment and for at least six months thereafter. These methods of contraception according to the note for guidance on non-clinical safety studies for the conduct of human trials for pharmaceuticals (CPMP/ICH/286/95, modification) include consistent and correct use of hormone containing implants and injectables, combined oral contraceptives, hormone containing intrauterine devices, barrier methods with spermicide, true sexual abstinence when this is in line with the preferred and usual lifestyle of the patient and partner with vasectomy. Periodic abstinence (e.g., calendar, ovulation, symptothermal, post-ovulation methods), declaration of abstinence for the duration of a trial, and withdrawal are not acceptable methods of contraception. If using hormonal contraception this method must be supplemented with a barrier method, preferably male condom (female condom and male condom should not be used together).

7.0 STUDY PROCEDURES

7.1 Schedule of Study Procedures

Study evaluations are summarized in the Table 9 and Table 10 below and described in Sections 7.2 through 7.2.7.

The Principal Investigator is responsible for ensuring that all staff involved in the study are familiar with the content of this section.

Table 9. Schedule of Study Evaluations in Arm A

	Pre-treatment 1	Cycle 1					Cycle 2 and subsequent cycles					EoT ¹⁴	FU ¹⁵
		1	2	3	4	5	1	2	3	4	5	25- 28	
Day													
Eligibility Criteria	X												
Registration/Randomization and Informed Consent	X												
Medical History	X	X*											
Quality of Life Questionnaires	X											X ¹⁰	X
Tumor Assessment ²	X											X	X
Physical Exam/ECOG	X	X*					X					X	X ¹¹
Vital Signs	X	X	X	X	X		X	X	X	X			
Hematology/Coagulation	X	X*					X*						X
Blood Chemistry	X	X*					X*						X
Creatinine Clearance	X												
CA-125		X*					X*					X	X ⁸
Urinalysis	X	X*					X*						
Serum Pregnancy Test (women of child bearing potential)	X												
LVEF ³	X						X ³						
ECG ⁴	X												X
Tumor Biopsy ⁵ (optional)	X			X									
Exploratory Biomarkers	X	X		X	X ¹³	X ⁷		X ⁷	X ^{7,13}			X	X ⁸
Administer APR-246		X	X	X	X		X	X	X	X			
Administer Chemotherapy				X					X				
Adverse Events and Concomitant Medication	X	X	X	X	X	X	X	X	X	X	X		
Survival				X									X ¹²
Pharmacokinetics ⁶		X	X	X									

Examinations marked * need not be repeated if already performed within 3 days prior to Day 1.

1. Pre-treatment evaluations are to be performed within 28 days of Day 1 of Cycle 1.
2. A CT scan/MRI should be performed at pre-treatment (within 4 weeks prior to day 1 of study treatment) and at the end of cycle 2 (within 7 days prior to the start of cycle 3), and at the end of cycle 4 (within 7 days prior to the start of cycle 5), after the last cycle, 2 months (\pm 2 weeks) after the end of treatment (EoT) visit and every 3 months (\pm 2 weeks) thereafter, until the documented disease progression, as determined by the Investigator at each site and defined by RECIST v1.1. Confirmatory scans to be done at least 28 days after scan performed post last treatment cycle for all patients initially assessed as having a radiological response.
3. LVEF assessed by echocardiography between day 21 of cycle 2 and start of cycle 3, and day 21 of cycle 4 and start of cycle 5. LVEF is mandatory before each additional administration of PLD that exceeds a lifetime cumulative anthracycline dose of 450 mg/m². Additional echocardiograms can be conducted if clinically indicated per institutional practices.

4. ECG will be monitored as per the standard of care for PLD treatment.
5. One tumor biopsy to be performed within 4 weeks prior to day 1 APR-246 infusion and one tumor biopsy to be performed cycle 1, day 3, per laboratory manual (optional).
6. For sparse PK sampling schedule on Cycle 1, days 1, 2, and 4, please refer to Section 8.4.
7. Only Cycle 2 day 1, 4, 5 and Cycle 6, day 1.
8. Blood samples should be taken at each follow up visit until progression, as per laboratory manual.
9. To be performed the first 4 follow up visits only.
10. QoL to be performed at each radiological tumor assessment time point.
11. Physical examination only, excludes ECOG.
12. Patients to be followed until death. Survival after progression will be monitored (e.g. via telephone, via General Practitioner or via review of medical records) every 6 months. The start date of the first subsequent treatment will be collected and recorded.
13. 18-72h after the end of infusion of APR-246.
14. End of treatment (EoT) visit should take place 7 days after the completion of 6 cycles of chemotherapy (between day 28 and day 35 of cycle 6) or up to 30 ± 2 days after the last administration of APR-246 if treatment is stopped early for any reasons.
15. The first follow-up visit should commence 2 months (± 2 weeks) after the EoT visit. Subsequent follow-up visits should be performed every 3 months (± 2 weeks) until documented disease progression as defined by RECIST v1.1.

Table 10. Schedule of Study Evaluations in Arm B

	Pre-treatment ¹	Cycle 1				Cycle 2 and subsequent cycles					EoT ¹³	FU ¹⁴
		1	2	3	4	1	2	3	4	25-28		
Day			1	2	3	4	1	2	3	4	25-28	
Eligibility Criteria	X											
Registration/Randomization and Informed Consent	X											
Medical History	X	X*										
Quality of Life Questionnaires	X										X ⁹	X X ⁸
Tumor Assessment ²	X										X	X X
Physical Exam/ECOG	X	X*				X					X	X ¹⁰
Vital Signs	X	X				X						
Hematology/Coagulation	X	X*				X*					X	
Blood Chemistry	X	X*				X*					X	
Creatinine Clearance	X											
CA-125		X*				X*					X	X ⁷
Urinalysis	X	X*				X*						
Serum Pregnancy Test (women of child bearing potential)	X											
LVEF ³	X					X ³						
ECG ⁴	X										X	
Tumor Biopsy (optional)	X ⁵											
Exploratory Biomarkers	X	X	X ¹²			X ⁶	X ^{6,12}				X	X ⁷
Administer Chemotherapy		X				X						
Adverse Events and Concomitant Medication	X	X	X			X	X	X	X	X	X	
Survival												X ¹¹

Examinations marked with * need not be repeated if already performed within 3 days prior to Day 1.

1. Pre-treatment evaluations are to be performed within 28 days of Day 1 of Cycle 1.
2. For patients in Arm B: A CT scan/MRI should be performed at pre-treatment (within 4 weeks prior to day 1 of chemotherapy administration) and at the end of cycle 2 (within 7 days prior to the start of cycle 3), and at the end of cycle 4 (within 7 days prior to the start of cycle 5), after the last cycle, 2 months (\pm 2 weeks) after the EoT visit and every 3 months (\pm 2 weeks) thereafter, until the documented disease progression, as determined by the Investigator at each site and defined by RECIST v1.1. Confirmatory scans to be done at least 28 days after scan performed post last treatment cycle for all patients initially assessed as having a radiological response.
3. LVEF assessed by echocardiography between day 21 of cycle 2 and start of cycle 3, and day 21 of cycle 4 and start of cycle 5. LVEF is mandatory before each additional administration of PLD that exceeds a lifetime cumulative anthracycline dose of 450 mg/m². Additional echocardiograms can be conducted if clinically indicated per institutional practices.
4. ECG will be monitored as per the standard of care for PLD treatment.
5. One tumor biopsy to be performed within 4 weeks prior to day 1 chemotherapy administration (optional).

6. Only cycle 2 days 1 and 2, and cycle 6 day 1.
7. Blood samples should be taken at each follow up visit until progression, as per laboratory manual.
8. To be performed at the first 4 follow up visits only.
9. QoL to be performed at each radiological disease assessment time point.
10. Physical examination only, excludes ECOG.
11. Patients to be followed until death. Survival after progression will be monitored (e.g. via telephone, via General Practitioner or via review of medical records) every 6 months. The start date of the first subsequent treatment will be collected and recorded.
12. 18-72h after the end of infusion of chemotherapy.
13. EoT visit should take place 7 days after the completion of 6 cycles of chemotherapy (between day 28 and day 35 of cycle 6) or up to 30 ± 2 days after the last administration of APR-246 if treatment is stopped early for any reasons.
14. The first follow-up visit should commence 2 months (± 2 weeks) after the EoT visit. Subsequent follow-up visits should be performed every 3 months (± 2 weeks) until documented disease progression as defined by RECIST v1.1.

7.2 Detailed Study Evaluations for Arm A and B

The following sections provide details of the study evaluations to be conducted pre-treatment, during study and in follow-up. Please refer to Table 9 for Arm A and Table 10 for Arm B for a complete schedule assessments required.

7.2.1 Registration /Informed Consent Form

Prior to performing any procedures or assessments, the nature of the study and the potential risks associated with the trial will be explained to all patient candidates and written informed consent will be obtained. Patients who choose to participate will have to consent to the biobanking program and will be asked to sign the mandatory section in the main study consent form related to biobank samples. Evaluations obtained as part of routine medical care and performed during the screening period may be used in place of the study specific evaluations. Patients will acknowledge and agree to the possible use of this information for the study by giving informed consent.

7.2.2 Pre-treatment

All pre-treatment evaluations are to be performed within 28 days of day 1 unless otherwise noted. Please see Table 9 and Table 10 for treatment windows for individual evaluations.

- **Eligibility criteria:** Including archived tumor sample review for positive IHC staining for p53.
- **Medical history.**
- **Quality of Life Questionnaires**
- **Tumor assessment:** CT scan/MRI.
- **Physical examination:** Height, weight, body surface area, and description of external signs of cancer.
- **ECOG performance status.**
- **Vital signs:** Heart rate, blood pressure, respiratory rate and temperature.
- **Hematology:** Hemoglobin, hematocrit, MCV, platelet count, WBC and WBC differentials.
- **Coagulation:** INR and APTT, if patient is receiving warfarin assessments should be done weekly.
- **Blood chemistry:** Sodium, potassium, calcium, magnesium, chloride, glucose, creatinine, total bilirubin, aspartate transaminase [AST], alanine transaminase [ALT], urea, total protein, albumin and lactic dehydrogenase [LDH], direct bilirubin and uric acid.
- **Creatinine clearance:** Calculated as per hospital practice.
- **Urinalysis:** Dipstick for protein, glucose, bilirubin and blood (perform microscopy if more than one positive dipstick test).
- **Serum pregnancy test:** For patients with reproductive potential.
- **LVEF:** Assessed by echocardiography within 4 weeks prior to Day 1. MUGA may be used

as an alternative.

- **ECG:** Standard 12-lead ECG.
- **Exploratory biomarkers:** Archive pathology samples and blood samples to be sent for p53 centralized analysis after registration. Refer to laboratory manual for detailed instructions.
- **Adverse events:** from the date the Informed Consent form is signed.
- **Concomitant medication.**

7.2.3 Randomization

- **Randomization:** Optimally performed prior to any biopsy. See Section 4.4 for procedure.
- **Tumor biopsy (optional):** Arm A tumor biopsy to be performed within 28 days prior to cycle 1 day 1 APR-246 infusion. Arm B tumor biopsy to be performed within 28 days prior to cycle 1 chemotherapy administration.

7.2.4 All Cycles, Days 1 - 28

Day 1 examinations marked * do not need to be repeated if already performed within 3 days prior to day 1 cycle 1.

- **Medical history:** Only cycle 1*.
- **QoL questionnaires:** To be completed at each radiological tumor assessment time point.
- **Tumor Assessments:** CT scan/MRI at the end of cycle 2 (within 7 days prior to the start of cycle 3) and at the end of cycle 4 (within 7 days prior to the start of cycle 5).
- **Physical examination:** Day 1*. Height, weight, body surface area, and description of external signs of cancer.
- **ECOG performance status:** Day 1.
- **Vital signs:** Arm A on Days 1, 2, 3 and 4. Arm B only on Day 1. Heart rate, blood pressure, respiratory rate and temperature.
- **Hematology:** Day 1* (repeat to follow up on AEs as appropriate). Hemoglobin, hematocrit, MCV, platelet count, WBC and WBC differentials.
- **Coagulation:** Day 1*. INR and APTT, if patient is receiving warfarin assessments should be done weekly.
- **Blood chemistry:** Day 1*. (repeat to follow up on AEs as appropriate). Sodium, potassium, calcium, magnesium, chloride, glucose, creatinine, total bilirubin, aspartate transaminase [AST], alanine transaminase [ALT], urea, total protein, albumin, lactic dehydrogenase [LDH], direct bilirubin and uric acid.
- **CA-125:** Day 1*
- **Urinalysis:** Day 1*. Dipstick for protein, glucose, bilirubin and blood (perform microscopy if more than one positive dipstick test).
- **LVEF:** Assessed by echocardiography between day 21 of cycle 2 and start of cycle 3, and day 21 of cycle 4 and start of cycle 5. LVEF is mandatory before each additional

administration of PLD that exceeds a lifetime cumulative anthracycline dose of 450 mg/m². Additional echocardiograms can be conducted if clinically indicated per institutional practices.

- **Tumor biopsy (optional):** Arm A only. One tumor biopsy to be performed optimally at the end of APR-246 infusion on day 3 of the first cycle, however a biopsy obtained at the end of the APR-246 infusion on day 2 is acceptable. Refer to laboratory manual for detailed instructions.
- **Pharmacokinetics:** Arm A only. On Cycle 1, days 1, 2, and 4; please refer to Section 8.4 for PK sampling time points.
- **Exploratory biomarkers:** Arm A blood samples. Cycle 1 on days 1, 4 and 5. Cycle 2 on days 1, 4 and 5. Cycle 6 on day 1. Arm B blood samples. Cycle 1 and 2 on days 1 and 2. Cycle 6 on day 1. Refer to laboratory manual for detailed instructions.
- **APR-246 administration:** Arm A only on days 1, 2, 3 and 4.
- **Chemotherapy administration (Carboplatin and PLD):** Arm A on day 4. Arm B on day 1.
- **Adverse Events:** All adverse events since the last visit should be recorded. Even though pre-medicated, patients should be closely monitored.
- **Concomitant medications.**

7.2.5 End of Treatment Visit

This visit should take place 7 days after the completion of 6 cycles of chemotherapy (between day 28 and day 35 of cycle 6) or up to 30 ± 2 days after the last administration of APR-246 if treatment is stopped early for any reasons.

- **Physical examination***: Height, weight, body surface area, and description of external signs of cancer.
- **QoL questionnaires**
- **Tumor Assessment:** CT scan/MRI. If the patient has stopped APR-246 treatment prior to completion of 6 cycles, tumor assessment should be performed at end of treatment visit if not done at the last cycle.
- **ECOG performance status.**
- **Hematology:** Hemoglobin, hematocrit, MCV, platelet count, WBC and WBC differentials.
- **Coagulation:** INR and APTT, if patient is receiving warfarin assessments should be done weekly.
- **Blood chemistry:** Sodium, potassium, calcium, magnesium, chloride, glucose, creatinine, total bilirubin, aspartate transaminase [AST], alanine transaminase [ALT], urea, total protein, albumin and lactic dehydrogenase [LDH], direct bilirubin and uric acid.
- **CA-125.**
- **ECG:** Standard 12-lead ECG.
- **Exploratory biomarkers:** Blood Sample. Refer to laboratory manual for detailed instructions.

7.2.6 Follow-up Visits

The first follow-up visit should commence 2 months (\pm 2 weeks) after the end of treatment visit. Subsequent follow-up visits should be performed every 3 months (\pm 2 weeks) until documented disease progression, as defined by RECIST v1.1.

- **Physical examination:** Description of external signs of cancer until progression.
- **QoL questionnaires (first four follow up visits only)**
- **CA-125:** Disease will be followed by GCIG Criteria until progressive disease and then confirmed by CT scan/MRI.
- **Exploratory biomarkers:** Blood samples taken at each visit until progression. Refer to laboratory manual for detailed instructions.
- **Tumor Assessment (by CT/MRI):** Tumor assessments by a CT scan/MRI will be performed 2 months (\pm 2 weeks) after the end of treatment visit and every 3 months (\pm 2 weeks) thereafter, until the documented disease progression, as defined by RECIST v1.1.

All patients will be followed until initial progression. Information on survival and subsequent therapies will be collected.

7.2.7 After Progression

Survival after progression will be monitored every 6 months. This can be done remotely (e.g. via telephone, via General Practitioner or via review of medical records). The start date of the first subsequent treatment will be collected and recorded.

7.3 Adverse Events

7.3.1 Definition of Adverse Events

An adverse event (AE) is the development of an undesirable medical condition or the deterioration of a pre-existing medical condition following or during exposure to a pharmaceutical product, whether or not considered causally related to the product. An undesirable medical condition can be symptoms (e.g., nausea, chest pain), signs (e.g., tachycardia, enlarged liver) or the abnormal results of an investigation (e.g., laboratory findings, electrocardiogram). In clinical studies, an AE can include an undesirable medical condition occurring at any time, including run-in or washout periods, even if no study treatment has been administered.

Any deterioration of the disease under study and associated symptoms or findings should not be regarded as an AE as far as the deterioration can be anticipated (see Section 7.3.3.8).

The term adverse event is used generally to include any AE whether serious or non-serious.

7.3.2 Definitions of Serious Adverse Events

A serious adverse event (SAE) is an AE occurring during any study phase (i.e., run-in, treatment, washout, follow-up), that fulfills one or more of the following criteria:

- Results in death
- Is immediately life-threatening (i.e., the patient was at risk of death at the time of the event. It does not refer to an event which hypothetically might have caused death if it was more severe)
- Requires in-patient hospitalization or prolongation of existing hospitalization, unless the hospitalization is for:
 - Routine treatment or monitoring of the disease under study, including hospitalization due to trial related procedures (e.g. APR-246 administration) not associated with any deterioration of the patient's status;
 - Elective treatment (planned before signing Informed Consent) for a pre-existing condition that is unrelated to the disease under study and has not worsened since signing Informed Consent;
 - Treatment on an emergency outpatient basis for an event not fulfilling any of the definitions for an SAE;
 - Social reasons, respite care in the absence of a medical condition.
- Results in persistent or significant disability/incapacity or substantial disruption of the ability to conduct normal life functions
- Is or results in a congenital abnormality or birth defect
- Is an important medical event (may not be immediately life-threatening or result in death or hospitalization) that may jeopardize the patient or may require medical intervention to prevent one of the outcomes listed above.

For further guidance on the definition of a SAE, see Section 7.3.3.10 below and also Appendix III of this Clinical Study Protocol.

7.3.3 Recording of Adverse Events

7.3.3.1 Time Period for Collection of Adverse Events

AEs will be collected throughout the study, from informed consent until 30 days after the last administration of study treatment.

SAEs occurring in this period should be reported to the Theradex® Safety Desk in the usual manner (see Section 7.3.4).

Events which are unequivocally due to a worsening of a patient's condition, attributable to the disease for which the investigational product is being studied, which occur after informed consent but before the patient is registered, should not be reported as an AE or SAE during the study.

7.3.3.2 Follow-up of Unresolved Adverse Events

All AEs should be followed until they are resolved or until the end of treatment (EoT) visit, whichever comes first. All AEs that are still ongoing after the EoT visit, should be followed on a regular basis, according to the Investigator's clinical judgment, until the event has resolved or until the Investigator assesses it as chronic and all queries have been resolved. After the EoT visit, AEs that are unrelated to APR-246 (serious or non-serious) or related but not serious, do not require further recording in the eCRF. For related SAEs that have been resolved, the event resolved date and the outcome of resolved or resolved with sequelae, as appropriate, should be recorded on the eCRF and the SAE Report Form. The Sponsor retains the right to request additional information for any patient with ongoing AE(s) at the end of the study, if judged necessary.

If an Investigator learns of any SAEs, including death, at any time following 30 days after the last administration of study treatment and he/she considers there is a reasonable possibility that the SAE is related to the study treatment, the Investigator should notify Theradex® Safety Desk.

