7.3.4 Reporting of Serious Adverse Events

All SAEs have to be reported to the Theradex® Safety Desk, whether or not considered causally related to the investigational product, or to the study procedure(s). All SAEs will be recorded in the eCRF.

If any SAE occurs in the course of the study (from signing of informed consent up to 30 days after last dose), then Investigators or other site personnel must inform the Theradex® Safety Desk

immediately, or **no later than 24 hours** of when he or she becomes aware of it.

For fatal or life-threatening adverse events where important or relevant information is missing, active follow-up is undertaken immediately. Investigators or other site personnel must inform the Theradex® Safety Desk of any follow-up information on a previously reported SAE immediately, or **no later than 24 hours** of when he or she becomes aware of it.

All SAEs require that a Serious Adverse Event Report Form be completed and forwarded either via fax or as a PDF via email to the Theradex® Safety Desk at the fax number or email listed below within 24 hours of becoming aware of the event. The fax and telephone numbers listed below may be used during both business and non-business hours. During non-business hours a recorded message will provide the caller with the contact information for the on-call monitor.

EU and US sites will report SAEs to:	Theradex® (Europe) Ltd. Safety Desk REDACTED
--------------------------------------	--

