9.5.1 Safety Analysis

Safety data will be summarized for the safety evaluable population. These data will include adverse events and laboratory parameters. Adverse event terms will be coded using the Medical Dictionary for Drug Regulatory Activities (MedDRA®, version 16.0 or higher). Adverse events will be summarized by body system, preferred term, severity, and relationship to treatment. Serious adverse events, deaths, and AEs leading to early discontinuation of study drug will be summarized. Laboratory parameters will be summarized by maximum NCI-CTCAE-4.0 severity grade and also by change from pre-treatment to scheduled time points using descriptive statistics. Laboratory parameter listings will include the normal ranges for each parameter. Each value will be classified as falling above, below, or within the normal range.

Data summaries will include only treatment-emergent adverse events (TEAEs), defined as events occurring on or after Day 1 Cycle 1 up to and including 30 days after last dose.

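### After the EoT visit, Section 7.3.3.2 lets eCRF updates of most ongoing AEs lapse, possibly before day 30, and its APR-246 relatedness test exempts every Arm B event

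*Combined protocol and SAP*

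**What the plan says.** Three sections count from the last dose:

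- Section 7.3.3.1: "AEs will be collected throughout the study, from informed consent until 30 days after the last administration of study treatment".
- Section 7.3.4: SAEs are reportable "from signing of informed consent up to 30 days after last dose", whatever their cause, and "All SAEs will be recorded in the eCRF".
- Section 9.5.1: treatment-emergent AEs (TEAEs) are "defined as events occurring on or after Day 1 Cycle 1 up to and including 30 days after last dose".

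Section 7.3.3.2, on follow-up of unresolved AEs, counts from the EoT visit. AEs ongoing after EoT are still followed clinically, but "AEs that are unrelated to APR-246 (serious or non-serious) or related but not serious, do not require further recording in the eCRF". The resolution date and outcome of a related SAE must still be entered.

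Section 7.2.5 sets EoT at 7 days after six completed cycles, with the range "between day 28 and day 35 of cycle 6". After an early stop, it gives only an upper limit of 30 ± 2 days from the last APR-246 dose. Table 10 footnote 13 repeats that anchor for Arm B, although Section 6.4.2 says Arm B gets no APR-246. The next visit is 2 months after EoT, and Section 7.2.6 lists no AE item for it.

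**The concern.** Two rules govern the same period. If EoT falls inside the 30 days, a site following 7.3.3.2 may stop updating an ongoing AE in the eCRF while 7.3.3.1, 7.3.4 and 9.5.1 still treat the window as open. For an unrelated SAE the conflict with 7.3.4 is direct.

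The exemption also depends on relatedness to APR-246, a drug given in one arm only, so the arms are held to different recording rules. Comparing the safety of the two regimens is a secondary objective (Section 3.1.2), and Section 9.5.1 tabulates AEs by severity and summarises SAEs. At stake is whether the final grade, seriousness and outcome of late ongoing events are captured alike in both arms.

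**Working it through.** **1. Can EoT fall before day 30 in patients who complete six cycles?**

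Inputs: the last dosing day of a cycle is Day 4 in Arm A and Day 1 in Arm B (Section 7.2.4); EoT is on Days 28 to 35 of cycle 6 (Section 7.2.5); the window is 30 days after the last dose.

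Window end = last dosing day + 30.
- Arm A: 4 + 30 = Day 34.
- Arm B: 1 + 30 = Day 31.

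Shortfall = max(0, window end − EoT day).

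| EoT on cycle-6 day | 28 | 29 | 30 | 31 | 32 | 33 | 34 | 35 |
|---|---|---|---|---|---|---|---|---|
| Arm A, days short | 6 | 5 | 4 | 3 | 2 | 1 | 0 | 0 |
| Arm B, days short | 3 | 2 | 1 | 0 | 0 | 0 | 0 | 0 |

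EoT is early on 6 of the 8 permitted days in Arm A and on 3 of 8 in Arm B. If visits were spread evenly over the eight days (an assumption), the mean shortfall would be 21/8 = 2.6 days in Arm A and 6/8 = 0.75 days in Arm B. At the stated target, 28 + 7 = Day 35, it is zero in both arms.

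**2. After an early stop**

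In Arm A, an EoT held 28 to 32 days after the last dose leaves 30 − 28 = 2 days short at most, and none from day 30 on. The text sets no earliest date, however. For illustration only, a visit 14 days after the last dose would leave 30 − 14 = 16 days, and one at 7 days would leave 30 − 7 = 23. The documents do not suggest either timing. In Arm B the timing is undefined, because there is no APR-246 dose to count from.

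**3. Who is exempt from further eCRF recording after EoT?**

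| Event ongoing at EoT | Arm A | Arm B |
|---|---|---|
| SAE related to APR-246 | Resolution date and outcome must be entered | Cannot occur |
| SAE related to chemotherapy only | Exempt | Exempt |
| Any other SAE | Exempt | Exempt |
| Non-serious AE | Exempt | Exempt |

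Every Arm B event is exempt. In Arm A the answer for an SAE depends on whether the investigator attributes it to APR-246. The causality text is itself mixed: Section 7.3.3.3 rates causality against the investigational product, while the question in Section 7.3.3.4 asks about study treatment.

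**4. What reaches the analysis?**

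Section 7.3.3.3 collects stop date, grade, seriousness and outcome for each AE. An AE ongoing at EoT that worsens or becomes serious before day 30 could be tabulated under Section 9.5.1 at its EoT status. An event that starts after EoT and by day 30 still falls under Section 7.3.3.1, and under 7.3.4 if serious.

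**The case against.** A reader might infer more: that recording of AEs in general ends at EoT, so that the TEAE tables cover different lengths of time by arm and the safety comparison is truncated. The documents do not support that. The section heading, the preceding sentence on AEs still ongoing after EoT, and the word *further* all confine the exemption to events already on record. Onset has its own rule in Section 7.3.3.1, and Section 9.5.1 defines TEAEs by when they occur, so a missing stop date or outcome removes no event from the count.

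Other points on that side also stand. The completer target of about Day 35 gives no loss. The ±2-day tolerance suggests that early-stop visits are meant to be near day 30. Section 7.3.4 requires follow-up information on any reported SAE to reach the Safety Desk within 24 hours, in either arm and whatever the cause. The second paragraph of 7.3.3.2 has the investigator notify later SAEs thought related to study treatment, which includes chemotherapy.

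These points do not remove the conflict. The Safety Desk duty does not oblige anyone to update the eCRF. The permitted EoT range still starts on Day 28, and the APR-246 test and the Arm B anchor are wrong on any reading. Although new onsets to day 30 are collectable, Section 7.2.6 gives no AE query at the next visit to pick them up.

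**Conclusion.** The point holds as a conflict between recording rules and as an unequal rule between arms. For completers, the conflict can last up to 6 days in Arm A and 3 in Arm B, and it is nil at the target visit day. After an early stop it is at most 2 days in Arm A if EoT is held at 28 to 32 days; the text sets no bound on an earlier visit, and Arm B timing is undefined. The relatedness inequality does not depend on when EoT takes place.

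The consequence is that grade, seriousness and outcome of AEs ongoing at EoT may be incomplete, and differently so by arm. It rests on two assumptions: that some EoT visits are held before day 30, and that a worsening AE is handled as an update of its existing record. The plan does not say whether it is an update or a new record. The documents give no event rates after EoT, so the size cannot be quantified. Nor can the direction: the possible day gap is larger in Arm A, while the exemption is wider in Arm B. No loss of new-onset TEAEs, and no bias in their counts, has been shown.

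**What to change.** - **Section 7.3.3.2, timing:** start the exemption at the later of the EoT visit and day 30 after the last dose of any study drug (APR-246, carboplatin or PLD). State that new onsets up to day 30 are recorded under 7.3.3.1.
- **Section 7.3.3.2, relatedness:** make the test relatedness to study treatment, so that SAE outcomes follow one rule in both arms. Align the causality variable in 7.3.3.3 with the study-treatment question in 7.3.3.4.
- **Section 7.2.5 and Table 10 footnote 13:** count the early-stop EoT visit from the last study treatment, so that it is defined in Arm B.
- **EoT before day 30:** ask about AEs that began or worsened up to day 30, by telephone once day 30 has passed or at the first follow-up visit.

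The cost is a wording amendment, slightly more AE data entry, and a short contact for patients whose EoT visit is early. No treatment or efficacy assessment changes.
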